
DATA COLLECTION & ANALYSES
	
Descriptive statistics will be performed using data collected from the health questionnaire and measures obtained from the medical testing. Demographic data of participants will be compared to 1996 Canadian census data to determine the extent in which the survey results can be generalized to the Port Colborne community. Response rates will be estimated across geographical regions of Port Colborne to evaluate the potential for response bias. Prevalence rates for selected health conditions will be summarized for the Port Colborne area, and where sample size permits, the rates will be compared across stratified sampling areas. Similarly, the occurrence of selected health conditions in Port Colborne will be compared to participants of the Canadian Community Health Survey, a recently conducted national health survey. Tests of significance, including confidence intervals will be presented for these comparisons. Multivariate methods will be used to adjust for differences in age and sex of the comparison populations.
 
Levels of the individual Chemicals of Concern, as determined by biological specimens analysis, will also be summarized. Variations in exposure levels within Port Colborne will be explored by calculating descriptive statistics, and through the use of multivariate analysis of variance methods. Logistic regression will be used to evaluate the relationship between the selected health conditions and exposure to Chemicals of Concern from both biological specimens and relevant questionnaire items of the health questionnaire. These models will provide odds ratios that will be adjusted for the effects of other potential confounding variables, such as age, sex, smoking habits, alcohol use and other indicators of socio-economic status. In addition, multivariate analysis of variance will be used to compare laboratory measures of Chemicals of Concern taken in Port Colborne residents to a normative sample, while adjusting for age and sex.

Abbreviations

ATSDR	Agency for Toxic Substances and Disease Registry
CBRA	Community-Based Risk Assessment
CCHS	Canadian Community Health Survey
CDC	Center for Disease Control
CHAP	Community Health Assessment Project
CO	Carbon Monoxide
COHb	Carboxyhaemoglobin
CoCs	Chemicals of Concern
CRF	Case Report Form
DLC	Differential Leukocyte Count
ECG	Electrocardiogram
ft4	Free Tetraiodothyronine (Thyroxine)
FEV1	Forced Expiratory Volume in 1 Second
FVC	Forced Vital Capacity
Hb	Haemoglobin

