in common, and a sample is drawn from within each stratum. In this study, the strata will be defined as geographic areas categorized by approximation to level of exposure to the chemicals of concern. Stratified random sampling has several advantages over random sampling alone. First, by stratifying it can be ensured that each subgroup of the population is represented and that the carefully designed allocation of subjects can permit comparisons across strata. Second, when the population can be subdivided into groups that are more homogeneous than the population as a whole, more precise estimates of population parameters are obtained than when a random sample is taken of the whole population. This is because the variance computed for the entire sample is based on each within-stratum variance. Finally, strata can be constructed so that those that may have the largest number of individuals of interest (i.e., those with high exposures) can be sampled most heavily (Kelsey et al., 1996).

In order to perform comparisons among those individuals with potentially higher levels of exposure, an “oversampling” of residents in the Rodney Street area of Port Colborne must be done. Specifically, a proportionally higher number of people in this area will be included in the study relative to other areas of the city. The inclusion of a larger subsample in this area will allow for analysis of the results within this stratum and for comparisons to be made between this stratum and the rest of Port Colborne. Thus, even though the health questionnaire and the medical testing will not necessarily be administered to all residents of the Rodney Street area, the sample that emerges from that area will be large enough to be representative of the whole Rodney Street area in the

same way that the total sample (after weighting to adjust for oversampling) will be representative of the whole population of Port Colborne.

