The estimated number of dwellings and individuals that make up the target population are listed in Table 1. This list is considered approximate as it is based on Canadian census data obtained in 1996.

Table 2: Estimated Number of Households and Individuals 12 years of Age and Older* within Each Sampling Region for the health questionnaire.

Region (EA's)	Number of private dwellings	Estimated population 12 years of age and older
1- West of the Welland Canal, south of Clarence and Augustine Road (151-156)	1,945	4,055
2- West of the Welland Canal, north of Clarence (116-120)	2,260	4,798
3- East of the Canal, south of Durham (includes Durham) and is bounded by Davis and Lake (110)	365	719
4 - East of the Canal, north of Durham (excludes Durham) and is bounded by Snider Road (106,108)	775	2,346
5- Other areas of Port Colborne (101-105,107,109,112-113)	2,030	4,437
Total	7,375	16,355

* assumes that 85% of the Port Colborne community is 12 years of age and older (based on 1996 Census data from Statistics Canada).

It is very important to note that while there are sufficient numbers to measure the prevalence of the selected health conditions with the desired precision, there is limited power to make comparisons between rates in the Rodney Street area to the remainder of Port Colborne. Specifically, with 500 subjects recruited in both the Rodney Street area and other parts of Port Colborne, the study has the power to detect an odds ratio of 2.1 for the comparison of asthma rates between the two regions with a power of 80% and a type I error rate of 5%. The odds ratio of 2.1 corresponds to a greater than two-fold increased prevalence rate in area 3 relative to the rest of Port Colborne. Similarly, for a comparison of nickel sensitivity rates in females between the two regions, there is power to detect an odds ratio of 2.2.

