6.3.1 CCHS Data

The Canadian Community Health Survey is an instrument used by Statistics Canada to collect health data at both the health region and province/territory levels. The survey targets persons 12 years or older, living in private dwellings in 10 provinces and 3 territories. Exclusions include persons in institutions, persons living on Indian Reserves or Crown lands, full-time members of the Canadian Armed Forces and residents of remote regions. The CCHS takes a representative sample of approximately 98% of the Canadian population aged 12 and older (over 130,000 nationwide, approximately 30,000 in the province of Ontario). The data is currently available for the content of the September 2000 version, and comparisons will be made to that data for Ontario.

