6.4 Statistical Analysis

The frequency distributions of variables collected within the health questionnaire and medical tests will be tabulated. The number of missing responses for each variable will be presented, and where possible, these missing values will be treated as a separate category. Particular attention will be given to examining response rates for income levels, since this variable will be used as a proxy to socioeconomic status. If necessary, other factors, such as education, may need to be used instead.

Prevalence rates for health conditions will be calculated by age-group for males and females. Statistically significant differences across strata will be evaluated by using the Chi-Square and likelihood ratio tests for categorical data, and the Student's t-test for continuous data. Multivariate analysis of variance will be used to adjust comparisons for the influence of potential confounding variables. Comparisons will need to take into account possible differences in the age and sex structure of the populations being compared. Of particular interest will be the comparison of Area 3 (otherwise known as the Rodney Street area) to the rest of Port Colborne. Comparisons will also be made to reference data for Ontario or other normative data.

To evaluate the potential influence for response bias, where possible, socio-economic characteristics will be compared between non-respondents and participants. These variables will include: age, sex, family size, income level, and neighborhood of residence. Statistical tests of significance will be performed to determine whether non-responders differed from those who participated in the survey. Response bias will also be examined by comparing survey results obtained from the 1996 Canadian census data.

The prevalence of selected health characteristics will be compared to responses obtained from participants of the 2000 CCHS. In order to control for differences in the underlying populations, direct standardization will adjust for the age and gender make-up of the populations being compared. The ratio of these standardized rates will be calculated, and

95% confidence intervals of this ratio will be used to assess statistically significant differences.

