Lifestyle and Dietary Information of Participants, by Sampling Areas,
CHAP Comprehensive Health Questionnaire, Fall 2002

	Area 3	Areas 1, 2, 4, 5	Total for Port Colborne	p-value [†]
	N (%)	N (%)	N (%)	
Occupation related to Exposure *				
Yes				
No				
Primary Source of Drinking Water				
Municipal				
Well				
Bottled				
Gardening Activity				
Yes				
No				
Non-occupational Activities related to Exposure to CoCs **				
Yes				
No				
Cigarette smoking status				
Never				
Current				
Former				
Unknown				
Exposure to second-hand Smoke				
Never				
As a child only				
As an adult only				
As a child and adult				
Current alcohol consumption				
Less than once a month				
1 To 3 times a month				
4 to 12 times a month				
> 12 times a month				
Jewelry piercings				
Yes				
No				

* Includes the following occupations: mining; metal cutting, grinding and refining; smelting; foundry work; steel making; welding; plumbing; brazing; plumbing; shipbuilding; metal plating or electroplating; boiler maker/repairer

** Includes painting, renovations, landscaping and automotive work

† p-value is based on Chi-square for comparison of proportions.

Table 5.
Prevalence of Selected Health Conditions of Participants, by Sampling Areas,
CHAP Comprehensive Health Questionnaire, Fall 2002

	Area 3	Areas 1, 2, 4, 5	Total for Port Colborne	p-value [†]
	N (%)	N (%)	N (%)	
Chronic Bronchitis				
Emphysema / Chronic Obstructive Pulmonary Disease				
Other Allergies				
Asthma				
Hypertension				
Heart Disease				
Thyroid Condition				
Stomach / Intestinal Ulcers				
Gastroenteritis				
Peripheral Neuropathy				
Arthritis				
Parkinson's				

[†] p-value is based on Chi-square for comparison of rates from Area 3 to Areas 1, 2, 4, and 5 after adjustment for differences in the age and sex distribution of the two populations.

Table 6.
External Comparison of Selected Health Conditions of Participants, by Sampling Areas,
CHAP Comprehensive Health Questionnaire, Fall 2002

	Port Colborne	Ontario	p-value [†]
	Prevalence	Prevalence	
Chronic Bronchitis			
Emphysema / Chronic Obstructive Pulmonary Disease			
Food Allergies			
Other Allergies			
Asthma			
Dermatitis			
High Blood Pressure			
Heart Disease			
Anaemia			
Thyroid Condition			
Stomach / Intestinal Ulcers			
Gastroenteritis			
Jaundice			
Parkinson's Disease			
Peripheral Neuropathy			
Parkinson's			

[†] p-value is based on Chi-square statistic of rates after direct standardization by age and sex. .

Table 7.

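### Table 6 bases the Ontario comparison on an unspecified chi-square instead of the ratio confidence interval set in 6.4; read as the ordinary test, its false-positive rate is about 15% at nominal 5%

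*Protocol*

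**What the plan says.** Three places in the protocol bear on this comparison.

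- **Section 6.4, Statistical Analysis.** For the CCHS comparison, "direct standardization will adjust for the age and gender make-up of the populations being compared". The ratio of the standardized rates is then formed, and the "95% confidence intervals of this ratio will be used to assess statistically significant differences".
- **Section 6.5.1, Table 6.** The table has a prevalence column for Port Colborne, one for Ontario, and a p-value. The footnote reads: "p-value is based on Chi-square statistic of rates after direct standardization by age and sex". There is no column for the ratio or its interval, although 6.5 says that the mock tables will carry the results proposed in the statistical section.
- **Synopsis, data collection and analyses.** "Tests of significance, including confidence intervals will be presented for these comparisons".

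The sampling design also matters. Section 6.1.1 works "with 500 subjects recruited in both the Rodney Street area and other parts of Port Colborne". Section 4.1 says that "the total sample (after weighting to adjust for oversampling) will be representative of the whole population of Port Colborne". Section 6.3.1 gives the comparator as "approximately 30,000 in the province of Ontario".

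**The concern.** The text and the table name different bases for calling the same result significant, and the table leaves out the quantity that the text makes decisive.

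The choice of chi-square has consequences. Wherever else the protocol describes a chi-square in enough detail to identify it, it is the ordinary test for categorical data or proportions (6.4; footnotes to Tables 3 and 4). A programmer working from the Table 6 footnote could reasonably apply that test to the standardized rates. Its variance is that of a simple proportion. A weighted, directly standardized rate from a sample that heavily over-represents one small area has a different variance.

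At stake are false signals in the mock table that compares disease prevalence in Port Colborne with Ontario, for a community already worried about its health. Table 6 lists 16 rows, one condition twice, so 15 distinct conditions. If all 15 were tested and none truly differed, about 15 × 0.05 = 0.75 would be flagged by a correct test, and about 15 × 0.145 = 2.2 by the ordinary chi-square.

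**Working it through.** **Figure to reproduce.** The protocol gives no power, precision or error figure for the Ontario comparison, so there is none to reproduce.

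**Inputs from the protocol**
- Allocation: 500 in Area 3 and 500 elsewhere (6.1.1).
- Population aged 12 and over: 719 in Area 3 of 16,355 in total (6.1.1, Table 2).
- Comparator: about 30,000 (6.3.1).
- Level: 5% two-sided, to match a 95% interval.

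**Assumptions**
- The four other areas are treated as one stratum, because their allocation is not given.
- Prevalence is similar in the two strata.
- The chi-square uses the raw n of 1,000.

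**Step 1: the two variances.** The ordinary chi-square uses p(1-p)/n. A directly standardized rate, Σ w_a p_a, has variance Σ w_a² p_a(1-p_a)/n_a over the age-sex strata. When areas are also weighted, each stratum term becomes w_a² Σ_h W_h² p_ah(1-p_ah)/n_ah, where W_h is the population share of area h.

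**Step 2: design effect of the area weights alone.**
- W_3 = 719/16,355 = 0.0440; the remainder is 0.9560.
- Design effect = n Σ W_h²/n_h = 1,000 × (0.0440²/500 + 0.9560²/500) = 2 × (0.0019 + 0.9140) = 1.83.
- Effective n = 1,000/1.832 = 546.

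**Step 3: actual error of the ordinary test.**
- With the Ontario rate taken as fixed: 1.96/√1.832 = 1.448, so the two-sided error is 14.8%.
- Allowing for 30,000 in Ontario: variance ratio = (1.832/1,000 + 1/30,000)/(1/1,000 + 1/30,000) = 1.805. Then 1.96/√1.805 = 1.459, and the error is 14.5%.
- With twice the female counts in 6.1.1 (2 × 234 = 468 and 2 × 251 = 502): design effect 1.77, effective n 548, error 13.8% to 14.1%.

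No age assumption enters steps 2 and 3.

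**Step 4: adding standardization (illustrative).** Age mixes and age-specific prevalences are not in the protocol, so they were assumed: five age bands; flat, asthma-like, blood-pressure-like and heart-disease-like prevalence profiles; and a Port Colborne age structure equal to, older than or much older than Ontario's. Each scenario had 40,000 simulated null data sets. The oversampled scenarios used only the older structure.

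| Test | Sample | Type I error at nominal 5% |
|---|---|---|
| Ordinary chi-square on standardized rates | Unweighted simple random sample | 1.5% to 10.5% |
| Ordinary chi-square on standardized rates | 500/500, area-weighted | 8.8% to 16.4% |
| (log ratio)²/stratum-based variance | All scenarios | 4.9% to 5.3% |

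The upper end of the second row includes runs with an assumed design effect of 2 for the Ontario survey. The third row is the test equivalent to the 6.4 interval and agrees with it by construction.

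**The case against.** The strongest reply is that the footnote never says the standardized rates are turned back into counts, or that the test is Pearson's. A one-degree-of-freedom chi-square using the variance of the standardized rates also fits the wording, holds its level, and matches the 6.4 interval. The synopsis plans tests and intervals together, and the variance formula could sit in an analysis plan that is not shown.

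Much of this stands. A reader might infer that Table 6 prescribes an invalid test, or that it necessarily contradicts 6.4. The protocol supports neither: the statistic is unspecified, and one reading of it is sound. What remains is that the only chi-square described elsewhere is the ordinary one, and that the shell has no place for the ratio and interval that 6.4 relies on.

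Three other inferences should be resisted.

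- **Errors in both directions**, with conditions of the young over-called and conditions of the old under-called. That pattern appears only in an unweighted sample under assumed age mixes. In every weighted 500/500 scenario tried, the ordinary test erred towards false positives.
- **Table 6 as the only comparison with people outside Port Colborne.** Sections 6.3.2 to 6.3.4 and 6.4 plan others, including a normative sample for metal levels.
- **The same fault in Table 5.** Its footnote, "p-value is based on Chi-square for comparison of rates from Area 3 to Areas 1, 2, 4, and 5 after adjustment for differences" in age and sex, fits a Mantel-Haenszel or logistic-model test and needs no change.

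**Conclusion.** The point holds as a mismatch between text and table with a material consequence under the more natural reading. Section 6.4 has a sound criterion; Table 6 replaces it with an unspecified chi-square and omits the ratio and its interval.

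If that chi-square is the ordinary one, the false-positive rate is about 15% at nominal 5% from the area weighting alone (13.8% to 14.8% across the allocations and comparator assumptions shown). This rests on the 500/500 allocation, the Table 2 populations, the weighting described in 4.1, similar prevalence across areas, and the remaining areas taken as one stratum. Standardization moves the figure further up or down by an amount that cannot be fixed from the protocol. If the chi-square is built on the variance of the weighted, standardized rates, there is no error in level, and only the missing columns and the unclear footnote remain.

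**What to change.** In Table 6:

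1. Replace the chi-square footnote with the 6.4 criterion: significance is judged by the 95% confidence interval of the standardized prevalence ratio.
2. Add two columns, one for the ratio (Port Colborne to Ontario) and one for its 95% interval.
3. State that the interval is computed on the log scale, with variance V_PC/R_PC² + V_ON/R_ON². Here R is a standardized rate and V its variance, built up from the age-sex strata; the Port Colborne term includes the area sampling weights.
4. If a p-value is kept, derive it from the same variance, as (log ratio)² divided by that variance on one degree of freedom, so that it cannot disagree with the interval.

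The cost is one footnote and two columns. No further data, subjects or measurements are needed, and the decision rule is already in 6.4.

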1.2.1.4 Arsenic (As)

The final CoCs of interest, arsenic, is a naturally occurring element widely distributed in the earth's crust. Exposure to higher than average levels of arsenic occurs mostly in the workplace, near hazardous waste sites, or in areas with high natural levels. Arsenic interferes with cellular metabolism on a number of levels, and can therefore affect many organ systems. Moreover, chronic arsenic exposure is linked to haematological conditions (eg. anemia); peripheral neuropathy (headache, numbness, weakness); gastroenterological illness; dermatological conditions (eg. hyperkeratosis; hypo- and hyper-pigmentation); and peripheral vascular disease (Ford et al., 1998; Abernathy, 1992; Aposhian, 1989; Schoolmeester and White, 1980).

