6.2.2.1 General medical laboratory screen tests

The general medical laboratory screen tests will include a number of measures that are based on the collection of blood and urine. Blood-based measures will include both haematology measures and biochemistry measures. Haematology outcome measures will provide concentrations, counts and volumes for blood-based parameters. Biochemistry outcome measures will include concentrations of total bilirubin, creatinine, blood urea nitrogen, cotinine, TSH and fT4. Urinalysis outcome measures will include presence of blood, leukocytes, protein, and glucose as well as nitrate concentrations and pH levels.

These measures will be expressed both in terms of mean values and within reference range frequency counts. Where the distribution of measured values are found to be non-normal, median values will be presented rather than means.

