6.2.2.2 Metal tests

The metal tests will assess levels of CoCs in blood or urine. Specifically, the mean specimen levels of nickel, copper, cobalt, and fractionated and non-fractionated arsenic will be evaluated. Three metal confounders will also be measured: mercury, lead and cadmium. Again, these measures will be expressed both as mean (or median) values and within reference range frequency counts.

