Comparison of the Mean Levels of Selected Biological Measures, by Sampling Areas,
CHAP Comprehensive Health Questionnaire, Fall 2002

	Area 3	Areas 1, 2, 4, 5	Total for Port Colborne	p-value [†]
	Mean (s.d)*	Mean (s.d)	Mean (s.d)*	
Haemoglobin				
White Blood Cell Count				
Red Blood Cell Count				
Haematocrit				
Mean Cell Volume of Red Cells				
Mean Hemoglobin Concentration of Red Cells				
Platelet Count				
Red Cell Distribution Width				
Mean Platelet Volume				
Differential Leukocyte Count				
Bilirubin				
Creatinine				
Plasma Cotinine				
Plasma Screen for Concentration of TSH				
Blood Urea Nitrogen				

[†] p-value is based on an ANOVA for comparing the means between Area 3, and Areas 1, 2, 4, and 5; after adjusting for difference in the age and sex distribution of the two populations.

* s.d. = standard deviation

Table 8.
Comparison of the Non-Specimen Tests Among Participants, by Sampling Areas,
CHAP Comprehensive Health Questionnaire, Fall 2002

	Area 3	Areas 1, 2, 4, 5	Total for Port Colborne	p-value [†]
	Mean (s.d) [*]	Mean (s.d)	Mean (s.d.)	
Calculated BMI				
Electrocardiogram	---	---	---	---
Blood Pressure				
Carbon Monoxide Breath Test				
Forced Expiratory Volume in 1 second				
Forced Vital Capacity				
Peak Expiratory Flow Rate				
Dermatology Patch: Nickel Sulfate				
Dermatology Patch: Cobalt Dichloride				

[†] p-value is based on an ANOVA for comparing the means between Area 3, and Areas 1, 2, 4, and 5; after adjusting for difference in the age and sex distribution of the two populations.

^{*} s.d. = standard deviation

Table 9.
Comparison of the Selected Measures of Chemicals Among Participants, by Sampling Areas, CHAP Comprehensive Health Questionnaire, Fall 2002

	Area 3	Areas 1, 2, 4, 5	Total for Port Colborne	p-value [†]
Chemical	Mean (s.d) [*]	Mean (s.d)	Mean (s.d)	
Nickel (Urine)				
Copper (Urine)				
Cobalt (Urine)				
Arsenic (Urine)				
Mercury (Urine)				
Lead (Blood)				

[†] p-value is based on an ANOVA for comparing the means between Area 3, and Areas 1, 2, 4, and 5; after adjusting for difference in the age and sex distribution of the two populations.

^{*} s.d. = standard deviation

Table 10.
Comparison of the Proportion of Tests Outside Normal Range for Selected Biological Measures,
by Sampling Areas,
CHAP Comprehensive Health Questionnaire, Fall 2002

	Area 3	Areas 1, 2, 4, 5	Total for Port Colborne	p-value [†]
Proportion Outside Normal Range				
Haemoglobin (normal range)				

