White Blood Cell Count (normal range)				
Red Blood Cell Count (normal range)				
Haematocrit (normal range)				
Mean Cell Volume of Red Cells (normal range)				
Mean Hemoglobin Concentration of Red Cells (normal range)				
Platelet Count (normal range)				
Red Cell Distribution Width (normal range)				
Mean Platelet Volume (normal range)				
Differential Leukocyte Count (normal range)				
Bilirubin (normal range)				
Creatinine (normal range)				
Plasma Cotinine (normal range)				
Plasma Screen for Concentration of TSH (normal range)				
Blood Urea Nitrogen (normal range)				

[†] p-value is based on logistic regression analysis controlling for differences in the age and sex distribution of the two sampling areas

Table 11.
Comparison of the Proportion of Non-specimen Tests Outside Normal Range, by Sampling Areas, CHAP Comprehensive Health Questionnaire, Fall 2002

	Area 3	Areas 1, 2, 4, 5	Total for Port Colborne	p-value [†]
Proportion Outside Normal Range				
Calculated BMI (average range)				
Electrocardiogram [‡]				
Blood Pressure (normal range)				
Carbon Monoxide Breath Test (normal range)				
Forced Expiratory Volume in 1 second (normal range)				
Forced Vital Capacity (normal range)				
Peak Expiratory Flow Rate (normal range)				
Dermatology Patch: Nickel Sulfate (normal range)				
Dermatology Patch: Cobalt Dichloride (normal range)				

[†] p-value is based on logistic regression analysis controlling for differences in the age and sex distribution of the two sampling areas

[‡] proportion with abnormal electrocardiogram

Table 12.
Comparison of the Proportion of Chemical Measures Outside Normal Range, by Sampling Areas, CHAP Comprehensive Health Questionnaire, Fall 2002

	Area 3	Areas 1, 2, 4, 5	Total for Port Colborne	p-value [†]
	Proportion Outside Normal Range			
Nickel (Urine) (normal range)				
Copper (Urine) (normal range)				
Cobalt (Urine) (normal range)				
Arsenic (Urine) (normal range)				
Mercury (Urine) (normal range)				
Lead (Blood) (normal range)				

[†] p-value is based on logistic regression analysis controlling for differences in the age and sex distribution of the two sampling areas.

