Arsenic Fractionation, Urine	Liquid-Liquid Extraction/Inductively Coupled Plasma-Mass Spectrometry (ICP-MS)	Urine	
 ▪ 10 mL from a 24-hour urine collection. No preservative. ▪ Collect in clean, plastic urine container(s) with no metal cap(s) or glued insert(s). ▪ Send specimen in a plastic, 13-mL urine tube or a clean, plastic aliquot container with no metal cap or glued insert. ▪ Refrigerate specimen within 4 hours of completion of 24-hour collection. Send specimen refrigerated. If the specimen is collected ambient and with no preservative, the specimen must be refrigerated or frozen for transport and storage. 	5.0 mL	Refrig\Frozen OK\Ambient\OK	
Inorganic (non-dietary) arsenic: <25 ug/specimen Values >= 25 ug/specimen are considered to be toxic concentrations
 
Note: The reference value is for a 24-hour collection.
 
Organic arsenic: All results are normal (reported as ug/specimen)

Copper, Urine	Inductively Coupled Plasma-Mass Spectrometry (ICP-MS)	Urine	
 ▪ 10 mL from a 24-hour urine collection. No preservative. ▪ Collect in clean, plastic urine container(s) with no metal cap(s) or glued insert(s). ▪ Send specimen in a plastic, 13-mL urine tube or in a clean, plastic aliquot container with no metal cap or glued insert. ▪ Refrigerate specimen within 4 hours of completion of 24-hour collection. Send specimen refrigerated. 	5.0 mL	Refrig\Frozen OK\Ambient NO	
15-60 ug/specimen
 
Note: The reference value is for a 24-hour collection.

Test Name	Methodology	Specimen Type	Specimen Required	Specimen Minimum Volume	Specimen Transport Temperature	Reference Values

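### Tables 10 and 12 count results below and above the reference range as one event, so for two-sided markers they cannot show the direction of an Area 3 difference

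*Protocol*

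**What the plan says.** Section 6.5.1 of the protocol lays out Table 10, a "Comparison of the Proportion of Tests Outside Normal Range for Selected Biological Measures", and Table 12, a "Comparison of the Proportion of Chemical Measures Outside Normal Range, by Sampling Areas". Each marker has a single row, for example "Copper (Urine) (normal range"), with one proportion for Area 3, one for Areas 1, 2, 4 and 5, and one for the city. The footnote to both tables gives the test: "p-value is based on logistic regression analysis controlling for differences in the age and sex distribution of the two sampling areas".

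The text defines the outcome in the same undivided way. Section 6.2.2.1 says of the laboratory screen: "These measures will be expressed both in terms of mean values and within reference range frequency counts". Section 6.2.2.2 says of the metals: "Again, these measures will be expressed both as mean (or median) values and within reference range frequency counts". Nowhere does the protocol separate low from high in these counts.

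The ranges are in the appendices. Appendix 10.4 gives two-sided adult ranges for seven of the fifteen Table 10 rows. Appendix 10.5 gives urine copper as "15-60 ug/specimen". The other five metals in Table 12 have in effect only an upper limit.

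**The concern.** The effects the protocol names have a direction. Section 1.2.1.4 states that "chronic arsenic exposure is linked to haematological conditions (eg. anemia"), which points to low haemoglobin. Section 1.2.1.3 raises altered thyroid function with cobalt, and low and high TSH are opposite findings. For the metals, the question is whether Area 3 has higher levels, yet a copper result under 15 is scored with a result over 60.

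Two things follow from merging the tails. If only one tail changes, the unaffected tail adds background events and dilutes the contrast. If the whole distribution shifts, one tail grows while the other shrinks, and the combined proportion moves less than either.

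The reader most affected is someone looking for anaemia by area. Table 5, the Area 3 comparison of reported conditions, has no anaemia row. The questionnaire in Appendix 10.1 has no anaemia item, only an open question on other long-term conditions. The frequency of low haemoglobin is therefore the obvious measure, and Table 10 does not isolate it.

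**Working it through.** The protocol gives no expected proportion or power for these outcomes, so there is no planned figure to reproduce. The size below is illustrative.

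**Inputs from the protocol**
- Two-sided ranges, adults (Appendix 10.4): haemoglobin 115–165 (F) and 130–174 (M) g/L; haematocrit 0.35–0.47 and 0.37–0.51; red cells 4.00–5.50 and 4.50–6.00; white cells 3.6–11.0; platelets 150–400; TSH 0.30–5.50; blood urea nitrogen 1.7–8.3.
- Bilirubin and creatinine start at 0, so they have no low tail.
- Metals (Appendix 10.5): copper 15–60. Upper limit only in effect: nickel 0–7, arsenic <120, mercury <10, cobalt <2, lead <20 (adults).
- Sample size (section 6.1.1): 500 v 500. The stated numbers of women with 50% female imply 234/0.5 = 468 v 251/0.5 = 502.
- Type I error 5% (section 6.1.1), taken as two-sided.

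**Assumption.** Normal distribution with 2.5% beyond each limit in the comparison area. Step 3 varies this.

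**Power formula.** Φ{[|p1−p2| − 1.96·√(p̄(1−p̄)(1/n1+1/n2))] / √(p1(1−p1)/n1 + p2(1−p2)/n2)}, unadjusted for age and sex.

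**Step 1: a 0.25 SD rise in Area 3**
- Above: 1 − Φ(1.96−0.25) = 0.0436. Below: Φ(−1.96−0.25) = 0.0136. Sum: 0.0572.
- Combined OR = (0.0572/0.9428)/(0.05/0.95) = 1.15.
- Upper-tail OR = (0.0436/0.9564)/(0.025/0.975) = 1.78.
- Power at 500 v 500: combined 7.3% (8.0% if rejections in the wrong direction are counted); upper tail 37%.

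**Step 2: low haemoglobin rises from 2.5% to 7.5%, upper tail unchanged at 2.5%**

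| n | low tail, 7.5% v 2.5% | combined, 10% v 5% |
|---|---|---|
| 500 v 500 | 95% | 85% |
| 468 v 502 | 95% | 84% |

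The odds ratio is 3.16 on the low tail and 2.11 combined. This is dilution, not cancellation.

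**Step 3: unequal tails at baseline, 0.3 SD rise**
- Upper tail 2.5% at baseline: 1 − Φ(1.96−0.3) = 4.8%.
- Lower tail 5% at baseline falls to 2.6%. Combined goes from 7.5% to 7.4%: full cancellation.
- Lower tail 10% at baseline falls to 5.7%. Combined goes from 12.5% to 10.5%: the wrong direction.

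**Step 4: copper**, assumed lognormal with 2.5% beyond each of 15 and 60
- Geometric mean √(15·60) = 30; log SD = ln(60/30)/1.96 = 0.354.
- A 10% rise in the geometric mean is a shift of ln(1.1)/0.354 = 0.27 SD. Below 1.3%, above 4.6% (unrounded 4.55%), combined 5.8%.
- Power at 500 v 500: 8% combined, 42% for results above 60.

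**Step 5: the planned comparison of means**, same 0.25 SD shift
- Φ(0.25/√(2/500) − 1.96) = Φ(1.99) = 98%.

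**The case against.** The strongest reply is that direction is already analysed elsewhere. Tables 7 and 9 compare age- and sex-adjusted means for the same markers. Section 6.4 adds upper and lower percentiles of each chemical of concern by area, and models health conditions by highest against lowest exposure tertile. For a pure shift, Step 5 shows the mean comparison far outperforms even the separated upper tail (98% against 37%). This stands, and it limits the point to Tables 10 and 12. A mean does not, however, report how many residents fall below the haemoglobin limit or above the copper limit, which is what these tables are for.

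Second, merging is not always worse. If both tails rise from 2.5% to 5%, the combined outcome has 85% power at 500 v 500, against 55% for either tail alone. That also stands. Section 3.2.2.1.1 treats both high and low haematology values as informative. Separate rows still show which is present.

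Third, mock tables may be refined in a later analysis plan. That is possible, but the protocol fixes the outcome and its test in the table titles and footnotes, and sections 6.2.2.1 and 6.2.2.2 repeat the undivided count.

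A reader might infer that incomplete 24-hour urine collections, by pushing copper below 15, would create a false Area 3 excess. The documents do not support this. Under-collection would have to differ between areas, and nothing suggests that it does. It would also lower the totals in Table 9 and the count above the limit, so splitting the tails would not cure it.

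**Conclusion.** The point holds, within limits. As written, Tables 10 and 12 cannot show whether Area 3 has more low haemoglobin, more high or low TSH, or more copper results above the limit. It affects seven of the fifteen rows in Table 10 and one of the six metals in Table 12.

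With 2.5% in each tail, a 0.25 SD rise appears as an odds ratio of 1.15 instead of 1.78. A tripling of low haemoglobin is diluted to about 84 to 85% power from about 95%, which is still above the 80% target used in section 6.1.1. These figures rest on assumed tail proportions and on normal (for copper, lognormal) distributions. The protocol gives no distributions for these markers.

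Two stronger readings are tempting. One is that opposite effects generally cancel: under equal tails the cancellation is only partial, and it becomes complete or reversed only where the low tail is the larger one, as in Step 3. The other is that the study would miss a directional difference altogether: Tables 7 and 9 and section 6.4 retain direction, so the documents do not support that.

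**What to change.** In Table 10, replace the single row for each of the seven two-sided markers with two rows, *below lower limit* and *above upper limit*, each with its own age- and sex-adjusted odds ratio. In Table 12, define the copper exposure comparison as results above the upper limit, and report results below 15 ug/specimen descriptively. Make the wording of sections 6.2.2.1 and 6.2.2.2 match.

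No new data are needed. The cost is more rows, more tests and sparser counts: at 2.5% per tail, 500 subjects give about 12 events per area (500 × 0.025 = 12.5), which is thin for an adjusted logistic model. If the two tails are each tested at 2.5% to allow for the extra test (2.24 in place of 1.96 in the power formula), power at 500 v 500 is about 27% for the upper tail in Step 1 and 92% for low haemoglobin in Step 2. Both remain above the combined outcome tested at 5%.
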